## LIST OF ABBREVIATIONS AND DEFINITION OF TERMS

AC	Analytic Core
AIDS	Acquired Immunodeficiency Syndrome
ART	Antiretroviral Therapy
ASO	AIDS Service Organization
ATN	Adolescent Medicine Trials Network for HIV/AIDS Interventions
CASI	Computer Assisted Self Interview
CDC	Centers for Disease Control and Prevention
CFR	Code of Federal Regulations
CRF	Case Report Form
DCF	Data Collection Form
DHHS	U.S. Department of Health and Human Services
EC	Ethics Committee
GC	Get Connected
GCP	Good Clinical Practices
HIPAA	Health Insurance Portability and Accountability Act
HIV	Human Immunodeficiency Virus
ICH	International Conference on Harmonization
IRB	Institutional Review Board
LGBTQ	Lesbian, Gay, Bisexual, Transgender, Queer
MC	Management Core
MTS	Michigan Tailoring System, a platform for eHealth interventions
NICHD	National Institute of Child Health and Development
NIDA	National Institute on Drug Abuse
NIH	National Institutes of Health
NSDUH	National Survey on Drug Use and Health
OHRP	Office for Human Research Protections
PI	Principal Investigator
PrEP	Pre-Exposure Prophylaxis
QNS	Query and Notification System
RDC	Remote Data Capture
SRV	Subject Recruitment Venue
STI	Sexually Transmitted Infection
TC	Technology Core
YMSM	Young Men who have Sex with Men

## STUDY ABSTRACT

- DESIGN:** *A two-arm prospective randomized controlled trial (RCT) in Philadelphia, Houston, and Atlanta. Participants randomized to the control condition will only see the site locator portion of the Get Connected intervention website. It will include information on HIV prevention services. Participants randomized to the intervention condition will receive tailored online content specific to their demographic characteristics (e.g., age, race/ethnicity, location, and relationship status), HIV/STI risk behaviors (e.g., HIV/STI testing history; substance use; communication with partners regarding status) and sociocultural context (e.g., homelessness, incarceration). We will also recruit, enroll, and train 10-15 mystery shoppers per city to conduct a mystery shopper assessment. Two mystery shoppers will visit each testing site separately and complete a standardized assessment of their visit. Site directors from 10 randomly selected testing sites in each city will be interviewed to assess sites' satisfaction with the biannual performance assessments and their improvements in service delivery when working with YMSM.*
- DURATION:** *Mystery shoppers are enrolled for approximately six months, or the time it takes them to complete approximately ten site visits. YMSM participating in the RCT are enrolled for 12 months.*
- SAMPLE SIZE:** *Total study sample size is 480 with the aim of maintaining a randomized sample of approximately 400 online-recruited and retained YMSM for 12 months. After consent, but prior to completion of the baseline survey, YMSM are randomized to either the intervention (n=240) or control (n=240) condition.*
- POPULATION:** *Individuals who were assigned male at birth and currently identify as male. 15-24 year-old (inclusive), self-report as HIV-negative or sero-status unaware, speak and read English, live in Philadelphia, Houston, or Atlanta, and meet one or both of the following high risk criteria: have not received HIV testing in past six months and/or report having consensual anal sex with a man in the past six months.*
- STRATIFICATION:** *Each site (Houston, Atlanta, and Philadelphia) will enroll 160 YMSM and 10-15 mystery shoppers.*

**DATA  
COLLECTION:**

*For study participants, we will use SurveyGizmo to collect YMSM's data. Online surveys allow participants to complete the survey at a convenient location, circumvent barriers (e.g., scheduling, transportation) and decrease social desirability. Participants may complete surveys on a mobile device or desktop or laptop computer on which they feel comfortable, or they may visit the subject recruitment venue (SRV). At baseline, participants will be logged into the SurveyGizmo assessment by site study staff. For follow-up assessments, participants will receive a unique link which will allow them to complete the surveys in multiple sittings or to resume a survey that has timed out or been closed. Mystery shoppers will use Qualtrics to complete an evaluation of each visited site. Interviews with agency directors will be audio-recorded to allow for verbatim transcription of the interview and checked for accuracy and completion.*

[figure not shown]
**OBJECTIVES**

*To test the efficacy of an e-Health intervention for increasing HIV-negative or HIV-unknown YMSM's successful uptake of HIV and STI testing willingness (e.g., routine HIV/STI testing) and PrEP awareness and willingness, as compared to the attention-control condition over a 12-month period.*

*To examine the quality of HIV test counseling and PrEP-related referrals to YMSM within local HIV/STI testing sites in 3 cities (Houston, Philadelphia, and Atlanta) through the use of mystery shoppers*

*Qualitatively assess testing sites' satisfaction with the biannual performance assessments and their improvements in service delivery when working with YMSM across the three regions.*

Study Design or Schema

Per the diagram above, the study is a two-arm randomized controlled trial. Once participants are proven eligible and they have provided informed consent, they will be randomized to one of two arms: intervention (Get Connected) and control (site locator portion of Get Connected). Participants randomized to the control condition will only have access to the site locator portion of Get Connected, with information on HIV prevention services. Participants randomized to the intervention condition will receive tailored online content specific to their demographic characteristics (e.g., age, race/ethnicity, location, and relationship status), HIV/STI risk behaviors (e.g., HIV/STI testing history; substance use; communication with partners regarding status), and sociocultural context (e.g., homelessness, incarceration). Five study assessments (surveys) are conducted at months 1, 3, 6, 9, and 12 for a total of 12 months follow-up for each arm.

## 1.0 INTRODUCTION

### 1.1 Background

In 2010, young men who have sex with men (YMSM) (aged 13-24) accounted for 30% of all new HIV infections among men who have sex with men (MSM). The HIV epidemic among YMSM is characterized by strong racial disparities; recent NHBS (National HIV Behavioral Surveillance) analysis showed 26% of African American MSM youth (18-24 years) tested HIV positive, compared to only 3% of White MSM 18-24 year olds. STI infections are also known to increase risk for HIV acquisition. With increasingly promising evidence of the efficacy of biomedical prevention tools, such as PrEP, for reducing risk of HIV infection among MSM, there is increased attention to the potential for HIV testing to act as a gateway to other HIV prevention tools and care efforts. Many of the cognitive and behavioral risk factors that contribute to the high rates of HIV infection among MSM are established during adolescence and the transition into young adulthood. This age group should be considered a priority time for intervening on cognitive and behavioral risks for HIV, while also introducing YMSM to HIV and STI testing as a gateway to other HIV prevention options. However, successful adoption of HIV prevention tools requires that YMSM overcome a series of multi-level barriers at the individual (e.g., risk awareness), systems (e.g., costs, lack of culturally competent care), and structural (e.g., homelessness, stigma) levels. Therefore, developing strategies to promote the use of HIV prevention services among YMSM requires the creation of interventions that are culturally sensitive to their psychosocial needs and facilitate access to comprehensive sexual health services.

### 1.2 Rationale

There is strong evidence of a significant and growing HIV epidemic among YMSM. From 2008–2011, YMSM aged 13–24 years had the greatest percentage increase (26%) in diagnosed HIV infections, with approximately 93% of all diagnosed HIV infections from male-to-male sexual contact. The HIV epidemic among YMSM is characterized by strong racial disparities. In an analysis of NHBS data from 2008-2014, Wejnert et al demonstrated that black MSM did not report greater sexual risks than other MSM, but were most likely to be infected with HIV and least likely to know it. Among black MSM aged 18–24 years tested in 2014, 26% were HIV positive, yet among white MSM aged 18–24 years tested in 2014, 3% were HIV positive. The disparity in HIV prevalence between black and white MSM increased from 2008 to 2014, especially among YMSM. YMSM now account for 72% of new infections among people ages 13 to 24, and 30% of all new infections among MSM. HIV prevention tools are needed that can address the unique developmentally specific prevention needs of YMSM, and that are culturally and developmentally adapted for this population in transition. Even if they were developmentally adapted, however, most of the existing evidence-based interventions (EBIs) for MSM (e.g., Many Men, Many Voices; MPowerment; d-up!) are delivered in face-to-face group settings. This creates a paradox: for many youth perceived or anticipated stigma, concerns over revelations of sexual or gender identity, and a lack of economic resources create barriers to YMSM attending the very interventions that are intended to reduce these barriers. Hence, *online delivered interventions may have a significant advantage for this population*, particularly

given that YMSM may not be able to access in-person EBIs in their communities, to attend sessions when they are offered, and to engage with the interventions' content when most convenient and appropriate.

A review of CDC's list of EBIs shows several interventions with efficacy for high-risk youth. Among these, *Assisting in Rehabilitating Kids (ARK)*, *Focus On Youth (FOY)*, *Becoming a Responsible Teen (BART)*, *iCuidate! (Take Care of Yourself)* and *Be Proud! Be Responsible* are all group delivered interventions, requiring youth to be physical and economically able to attend a group setting, and comfortable with discussing sensitive issues in groups of their peers. The only one-on-one intervention for YMSM classified as an EBI is *Choosing Life: Empowerment, Actions and Results (CLEAR)*, but this is specific to improving ART adherence among YMSM living with HIV. Absent from the list of youth-focused EBIs is an online intervention for YMSM that surmounts the barriers associated with attending HIV services, and focuses on creating shifts in cognitive and behavioral HIV-related outcomes for YMSM. If proven efficacious, the proposed intervention – *Get Connected* – can fill this gap by providing an e-delivered, tailored intervention that allows YMSM to learn about local prevention services and build the skills necessary for successful adoption of prevention.

#### 1.2.1 Repeat HIV/STI testing has the potential to reduce HIV testing by increasing knowledge of sero-status and act as a gateway to other prevention options

In light of the high incidence of HIV among YMSM, creating behavioral shifts towards routine HIV testing must be considered a priority goal. Among the drivers of the HIV epidemic among YMSM are large numbers of HIV positive youth who are not virally suppressed and/or are not aware of their sero-status. Increasing HIV testing among YMSM should thus be considered a public health priority. The success of the National HIV/AIDS Strategy's test and treat approach rests on the ability to increase the number of YMSM who receive routine testing. Getting tested is the cornerstone of almost all prevention approaches and the gateway to both biomedical preventions tools (e.g., PrEP) and to HIV care for those who test positive. Successful engagement in HIV prevention for HIV negative youth (routine HIV testing, consistent condom use, PrEP adoption) and care services for HIV positive youth (e.g., linkage and retention in care; access to ART to promote viral suppression) requires that YMSM overcome a series of multi-level barriers at the individual (e.g., risk awareness, self-efficacy to get tested), systems (e.g., costs, medical mistrust, lack of culturally competent care), and structural (e.g., homelessness, costs, stigma) levels. Therefore, developing strategies to promote HIV/STI status awareness among YMSM requires the creation of interventions that are culturally sensitive to the psychosocial needs of YMSM and facilitate access to comprehensive sexual health services. *In response to these challenges, our intervention recognizes that it is important to activate our target population's awareness of their increased risk and readiness to learn about prevention strategies prior to linking them to services.*

#### 1.2.2 Online delivered HIV prevention interventions are ideal to reach and engage YMSM in conversations about their HIV risks

Given youths' increased use of online media in their day-to-day exchanges, online interventions have numerous advantages over in-person delivered interventions. Online interventions are a promising mode of HIV/STI prevention given their ability to deliver responsive and interactive content specific to each user's characteristics (i.e., tailored content), with extended reach across geographic regions and increased convenience to access content at any time through tablets,

laptops, and smartphones. Furthermore, online content can be refreshed to be contextually-responsive over time, particularly as YMSM become sexually-active, meet new partners and/or engage in different risk behaviors. Delivery of online content may also ensure higher intervention fidelity and may be accessed through smartphones if YMSM are unable to afford internet-based connectivity due to socioeconomic barriers. Data from the 2015 Pew Teens & Technology Surveys, noted that 92% of teens go online daily. Internet use among youth in the U.S. was near 97% in 2014, with more than 70% of youth having broadband at home and/or connecting via a mobile device. Although Whites (91%) are more likely than Blacks or Latinos to report owning a desktop or laptop computer (~80% each), Black teens are more likely to own a smartphone (85%) and go online through a mobile device (100%) than Whites (71% ownership, 90% access). Collocating online interventions is also important as YMSM often rank the web as their top resource to access comprehensive sexual education, learn about their sexuality and sexual behavior, and meet partners.

### 1.2.3 Test locators are becoming increasingly popular as a means of linkage to care

Researchers and practitioners have sought to encourage timely and repeated HIV/STI testing by creating online tools that provide the location of testing centers in a given geographic area (i.e., test locators). These testing locator interventions have demonstrated wide reach when evaluated (e.g., AIDS.gov test locator had over 16,000 searches and was adopted by over 100 websites in its first year); however, there are no peer-reviewed published data examining the appeal of these locators within YMSM populations specifically or the quality and adequacy of these listed sites for YMSM. This is concerning for several reasons. First, it is expected that testing agencies are youth and LGBTQ (i.e., lesbian, gay, bisexual, transgender and/or queer) friendly, but there is little empirical evidence to support this assumption, and in fact evidence to support the contrary. Second, our efforts to encourage and motivate YMSM to engage in repeat HIV/STI testing or to adopt other prevention efforts (e.g. PrEP) may be diminished if structural barriers (e.g., medical mistrust, lack of insurance or transportation) and cultural insensitivity to YMSM's needs (e.g., racial/ethnic and sexual orientation stigma) lead to delays or avoidance of HIV/STI services. *The GC intervention seeks to address these systemic challenges by providing a test locator that accounts for sites' quality of HIV prevention service delivery and their ability to cater to YMSM's needs.*

Building on the efficacy of the CDC's Project Connect Health Systems Intervention to link heterosexual adolescents to competent comprehensive sexual health care services, we developed *Get Connected* (GC), an online brief intervention that employs individual and systems-level tailoring technology to reduce barriers to HIV prevention care (e.g., HIV/STI testing, PrEP) for YMSM. The deployment of GC through a mobile-friendly WebApp seeks to optimize online interventions' acceptability, accessibility, availability, and long-term affordability among youth. GC was developed for YMSM (ages 15-24) through a community-based participatory research approach that included a rapid assessment of existing HIV services through a mystery shopper methodology, and the creative input of scientists, service providers, and YMSM. Data from our pilot RCT (N=130 YMSM; ages 15-24) indicated high acceptability and feasibility for GC, and clinically meaningful effect sizes (ES) in self-efficacy to discuss HIV testing with partners (ES=.50-.64), trust in their providers (ES= .33-.35), reductions in number of sexual partners (ES=.21), and HIV/STI testing behavior (ES=.34; 30% of participants tested for HIV/STIs) at the 30-day post-intervention follow-up.

## 2.0 STUDY OBJECTIVES

As part of the U19 project, we propose to test the efficacy of Get Connected (GC) for increasing HIV-negative or sero-status unaware YMSM's successful uptake of HIV and STI testing willingness (HIV and STI testing). Given the overall low level of PrEP awareness and use among YMSM currently, we also include awareness of and willingness to use PrEP as a primary outcome (PrEP uptake during the trial will be measured as a secondary outcome). At the agency level, HIV/STI testing sites listed in GC will receive biannual performance assessments based on ratings that YMSM provide after visiting their locations. We will examine improvements in the quality of HIV test counseling and PrEP-related referrals to YMSM accessing local HIV/STI testing sites in the 3 cities selected to test GC.

### 2.1 Primary Objective:

Test the efficacy of GC for increasing HIV-negative or HIV-unknown YMSM's successful uptake of HIV and STI testing (e.g., routine HIV/STI testing) and increase in PrEP awareness and willingness, as compared to the attention-control condition over a 12-month period.

### 2.2 Secondary Objective:

Examine the quality of HIV test counseling and PrEP-related referrals to YMSM within local HIV/STI testing sites in 3 cities (Houston, Philadelphia, and Atlanta) through the use of mystery shoppers.

### 2.3 Tertiary Objective:

Qualitatively assess testing sites' satisfaction with the biannual performance assessments and their improvements in service delivery when working with YMSM across the three regions.

### 2.4 Study Hypotheses/Research Questions

- *Relative to the control condition, YMSM exposed to the GC intervention will report significantly greater increases in routine HIV/STI testing over a 12-month period. HIV testing will be the primary outcome for the trial.*
- *Relative to the control condition, YMSM exposed to the GC intervention will report increases in motivation around HIV testing (conceptualized as HIV/STI testing intentions, self-efficacy to engage in HIV/STI testing, and overcoming testing-related barriers).*
- *Relative to the control condition, YMSM exposed to the GC intervention will report significantly greater PrEP awareness and willingness to use PrEP).*

The primary analyses of the data from the Get Connected 2-parallel group randomized clinical trial will be performed according to the participants' original treatment assignment (i.e., intention-

to-treat analyses) and the inclusion of all data from all participants randomized in the final analysis.

### **Binary outcomes such as HIV testing:**

The percentage of participants who report routine HIV testing over a 12-month period will be compared between the intervention arms (GC and the Control condition). Five assessments will occur at 1 month (visit window  $\pm$  1 month), 3 months ( $\pm$  1 month), 6 months ( $\pm$  1 month), 9 months ( $\pm$  1 month), and 12 months ( $\pm$  1 month). Repeated-measures analyses for HIV testing will be implemented by performing a generalized estimating equations (GEE) analysis via the SAS GENMOD Procedure (version 9.4; SAS Institute, Cary, NC) with an exchangeable correlation structure for the repeated measures within participant (binomial-logit model). The statistical model will include three predictors (intervention arm, time on study and the statistical interaction between intervention arm and time on study). The statistical model will provide estimates of the percentages of participants reporting HIV testing (plus 95% confidence intervals) by intervention arm and time on study. The model-based estimates are unbiased with unbalanced and missing data, so long as the missing data are non-informative (missing completely at random, MCAR). A P value  $\leq 0.05$  will be considered statistically significant for the main effects (intervention and time on study) and for the intervention by time on study interaction effect from the repeated measures analysis. **The statistical test for interaction between time on study and intervention arm will be the primary overall hypothesis test to determine whether HIV testing in the intervention groups changed in significantly different ways during follow-up (i.e., different temporal patterns over time).** If HIV testing rates in the two intervention groups are consistently different or similar (i.e., no statistical interaction) then the main effect test for intervention will be used as the primary test of intervention efficacy. If a significant interaction is detected, then Wald chi-square tests will be used to compare the differences between the model-based HIV testing estimates at each time interval and to compare differences over time within each intervention arm. Specific statistical tests will be done within the framework of the generalized linear model. All statistical tests will be 2-sided and unadjusted for multiple comparisons.

The primary assessment for a difference between intervention arms for 'frequent tester' rates will be a two-sided Z-test for independent proportions with pooled variance. Confidence intervals (95%) will also be reported for the observed difference between the GC and control arms in 'frequent tester' rates. The same analysis plan described above will be used for the other primary outcomes that as binary (i.e., STI testing, PrEP awareness).

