### 3.4 Study Randomization, Stratification, or Description of Non-Random Assignment Procedures

For the primary objective, participants will be randomly assigned to one of two groups, stratified by city/SRV site: intervention and control. After consent, YMSM are randomized to either the control or intervention condition (Intervention, n=240; Control, n=240). **We intend to blind participants to the intervention arm assignment in order to improve the internal validity of the study, the rigor of the assessment of outcomes, and to minimize bias due to awareness of treatment assignment.**

For the secondary objective, mystery shoppers will visit testing sites that have been randomized such that each site has an equal likelihood of being shopped on any given day at any given time (during normal operating hours).

For the tertiary objective, participants will be randomly selected from participating HIV testing sites in each of the three cities. Only sites that have been visited and assessed by study participants will be included in each city's sample for randomization.

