## **5.3 Randomization Procedures**

For the primary objective, after consent, YMSM are randomized to either the control or intervention condition, stratified by city/SRV site (Intervention, n=240; Control, n=240). Participants will be randomized on a 1:1 basis to either the control or intervention arm.

For the secondary objective, testing sites are randomized by day of the week and time of day. After consent and training, participants will work with study staff to find day and time slots for their site visits.

For the tertiary objective, 10 eligible testing sites in each city will be randomly selected. The site director for those sites will be contacted for an interview.

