### 5.4.2 Mystery Shoppers

Two mystery shoppers will visit each location separately. Each HIV/STI/PrEP clinic will require two round-trip visits during the mystery shopper phase. There are up to 60 registered HIV testing sites offering free HIV tests for men within each city's 25-mile radius: Atlanta (up to 20 sites), Houston (up to 26 sites), and Philadelphia (up to 55 sites). We will use time space sampling to ensure that varying days (weekdays versus weekends when applicable) and times (e.g., morning versus afternoon or evening) are selected for visits, thereby maximizing the chance of getting different counselors at each agency. The project manager will create a calendar for mystery shoppers to know when and where they will be getting tested. We will reimburse the mystery shoppers for all charges linked to their testing experiences. Mystery shoppers will be instructed to be honest about their sexual behaviors during their visits. By avoiding creating 'personas' or 'scripts,' shoppers will increase the social validity of the assessment and avoid arousing suspicion due to exaggerated or unrealistic scenarios. Upon completion of a testing visit, the mystery shoppers will complete the Qualtrics site follow-up survey immediately. Mystery shoppers will also be asked to summarize their qualitative impressions using an open text field.

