## 10.3 Statistical Analysis Plan

10.3.1 We will use the general framework of generalized linear mixed models (GLMM) to test for intervention effects over time. Note that some of our outcomes are binary, some count and some continuous traits, and thus need to be treated differently. The general form of the GLMM will be  $g(\mu_{ij}) = \beta_0 i + \beta_{cov} Covariates_{ij} + \beta_{Time} j + \beta_{Trt} Trt_{Armi} + \beta_{Arm \times Time}$ , where  $\beta$  is the mean response corresponding to subject  $i$  at Time  $j$  (baseline and 4 follow-ups), with its appropriate link function (identity for continuous outcome, logit for binary outcome and natural log for count outcomes);  $Trt = 1$  if the  $i$ -th subject is in the intervention group and 0 if the  $i$ -th subject is in the attention-control group. The interaction coefficients are of interest here, measuring the difference in the rate of change in outcome across the two treatment groups over time. The subject-specific random intercepts are assumed to be normally distributed with a common variance and they account for within-person correlation. We will also explore if we need a subject-specific random-slope corresponding to visit in the above model. Maximum likelihood estimation will be used for fixed effect parameters. Models will be compared according to information criterion like AIC, BIC. For some binary outcomes like HIV testing, we will perform an aggregate analysis after collapsing across the repeated measures using simple logistic regression comparing whether the probability of having tested at least once over the entire FU period is different across treatment groups, after adjusting for baseline values. To ensure robustness, we will also apply an exchangeable working correlation structure to its corresponding generalized estimating equation (GEE) model. We will also conduct exploratory regression analyses to examine city differences in the outcomes. These regressions will be run with group assignment and city in the model, controlling for socio-demographic characteristics.

Interactions between group assignment and city will be tested to explore potential site-specific moderators of treatment effect.

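### Randomisation is stratified by city, but the frequent-tester Z-test and the arm main effects leave city out; if testing rates differ by city, some power is given up

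*Combined protocol and SAP*

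**What the plan says.** **Design.** Section 3.4 states that "participants will be randomly assigned to one of two groups, stratified by city/SRV site: intervention and control". Section 5.3 repeats the stratification and adds: "Participants will be randomized on a 1:1 basis to either the control or intervention arm". The Study Abstract sets equal strata: "Each site (Houston, Atlanta, and Philadelphia) will enroll 160 YMSM and 10-15 mystery shoppers". Neither 3.4 nor 5.3 describes blocking or any other way of holding the arms level within a city.

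**Primary analyses (section 2.4).**
- HIV testing as a repeated binary outcome uses a logit GEE: "The statistical model will include three predictors (intervention arm, time on study and the statistical interaction between intervention arm and time on study"). Arm-by-time is tested first. The arm main effect becomes the primary efficacy test if there is no interaction.
- The frequent-tester outcome, which section 10.2 uses for power, is compared by "a two-sided Z-test for independent proportions with pooled variance". The same plan covers STI testing and PrEP awareness.
- Continuous outcomes use a MIXED model with the same three predictors and the same order of tests.

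**City elsewhere.** Section 10.3 says: "We will also conduct exploratory regression analyses to examine city differences in the outcomes". It also plans arm-by-city interactions. The covariate term of the GLMM in 10.3.1 is not itemised, and the adjusted runs in 10.1.1 do not list city.

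**The concern.** The usual rule is to analyse by the factors used to stratify the randomisation. When arms are balanced within city, differences between cities cannot move the arm contrast. A pooled-variance Z-test still counts that variation as noise, so its standard error is too large and the test is conservative. When arms are not forced to balance within city, the unadjusted standard error is correct, but a stratified comparison is still more precise if city predicts testing.

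What is at stake is power on the outcome that the trial was sized for, and on the arm main effect when that becomes the efficacy test. There is little slack. Section 10.2 requires 400 analysed participants, and 480 with the projected 20% attrition (section 3.1, Phase 1c) leaves 384.

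**Working it through.** **Inputs from the documents.** Two-sided alpha 0.05, 80% power, 400 analysed and a 13-point difference (10.2); three equal cities of 160 (Study Abstract).

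**Assumed.** Control rate and city rates. Section 10.2 states no control rate. The nearest testing figure is the pilot's 30% at 30 days (1.2.3).

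**1. The plan's own figure.** For 25% against 38%, the mean is 0.315 and

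n per arm = [1.96·√(2·0.315·0.685) + 0.842·√(0.25·0.75 + 0.38·0.62)]² / 0.13² ≈ 199.2, that is 200 per arm or 400 in all.

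This is a back-solve for the control rate. At 20% the answer is 180 per arm, and at 30% it is 215.

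**2. Excess standard error and type I error of the Z-test, arms balanced within city.** With p̄ the mean rate and p_c the city rates,

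ratio = √[ p̄(1−p̄) / mean of p_c(1−p_c) ]; type I error = 2·P(Z > 1.96 × ratio).

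For 15/30/45%: √(0.210/0.195) = 1.038, and 2·P(Z > 2.034) = 4.2%.

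**3. Power, 200 per arm, 13 points in every city, mean control rate 30% (overall mean 0.365).**
- Pooled null SE = √(2·0.365·0.635/200) = 0.0481.
- True SE of the difference, balanced within city = √{[mean of p_c(1−p_c) + mean of p_t(1−p_t)]/200}, where p_t is the intervention rate in each city. For 15/30/45% this is √[(0.1950 + 0.2301)/200] = 0.0461.
- Z-test power = Φ[(0.13 − 1.96·0.0481)/0.0461] = 78.0%.
- The stratified test uses a within-city null SE of √(2·0.2168/200) = 0.0466. Power = Φ[(0.13 − 1.96·0.0466)/0.0461] = 80.0%.

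| City control rates | SE ratio under the null | Type I error of Z-test | Z-test power | Stratified power | Gain (points) |
|---|---|---|---|---|---|
| 25/30/35% | 1.004 | 4.9% | 77.33% | 77.55% | 0.2 |
| 20/30/40% | 1.016 | 4.6% | 77.59% | 78.45% | 0.9 |
| 15/30/45% | 1.038 | 4.2% | 78.03% | 79.97% | 1.9 |
| 10/30/50% | 1.070 | 3.6% | 78.68% | 82.12% | 3.4 |

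A simulation of the Z-test against the Cochran-Mantel-Haenszel test (40,000 trials per setting) gave gains of 0.3, 1.0, 1.8 and 3.4 points. With a 25% mean rate the analytic gains are 0.3, 0.9, 1.9 and 3.3.

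**4. Simple randomisation within city.** The Z-test's type I error stays at 5% and its power at 77.3% whatever the spread. At ±10 points the stratified test has 78.4%, a gap of about 1.1 points.

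**5. After attrition (192 per arm).** At 15/30/45%, balanced, power is 76.3% unstratified and 78.3% stratified. At 10/30/50% it is 76.9% and 80.6%.

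**6. GEE.** A small simulation (150 trials per setting, Monte Carlo error about 3 to 4 points per figure) compared fits without and with city.
- Arm-by-time: power 44% against 45% at a city shift of 0.5 logit, and 43% against 44% at 1.0. The standard error of the last interaction contrast rose at 1.0 logit, from 0.276 to 0.303.
- Arm main effect: 77% against 78% at 0.5 logit, and 74% against 87% at 1.0. The direction agrees with the Z-test, but the second gain is too noisy, and the shift too large, to serve as an estimate.

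**The case against.** Three stronger readings are tempting, and the documents do not support them.

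*The error bars of the primary tests in general are too wide.* The first GEE and MIXED test is arm-by-time. That is a within-person contrast, and a city main effect barely alters it. In the logit model its standard error need not shrink at all, because odds ratios are non-collapsible. Even for the Z-test, an oversized standard error requires balance within city, which no described procedure secures and which attrition may loosen.

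*The cities differ greatly in access to testing.* The only evidence is a count of free sites: "Atlanta (up to 20 sites), Houston (up to 26 sites), and Philadelphia (up to 55 sites") in section 5.4.2. These are upper limits, not per head, and not testing rates. At ±5 points the issue almost vanishes.

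*Adding city costs nothing.* Section 2.4 promises model-based percentages by arm and time. With city in a logit model these need a standardisation rule, and the odds ratio becomes conditional on city.

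It is also fair to say that the loss is small, that it lies on the safe side, and that 10.3 will already produce models with arm and city. All of this limits the point without removing it. The city models are exploratory, so the primary tests remain unstratified. Having both results without a pre-specified choice between them also invites a choice after the fact.

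**Conclusion.** The point stands as a modest efficiency gap in the frequent-tester Z-test, in the other binary primary outcomes tested the same way, and in the arm main effects of the GEE and MIXED models. For the Z-test the loss is under 1 point of power for city spreads up to ±10 points, about 2 points at ±15 and about 3.4 at ±20. This assumes 200 per arm, a 13-point effect in every city, a mean control rate near 30% and balance within city.

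The type I error of 4.9% to 3.6% also depends on that balance. Without it the test keeps its 5% level and only efficiency is lost. Whether city rates differ by these amounts cannot be settled from the documents. Nothing here biases the comparison, raises the false-positive risk or weakens the arm-by-time test.

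**What to change.** - **Binary primary outcomes now given the pooled Z-test:** replace it with a Cochran-Mantel-Haenszel test stratified by city, and report a Mantel-Haenszel risk difference with 95% CI.
- **GEE and MIXED models:** add city (three levels) as a fixed effect.
- **GEE reporting:** give the percentages by arm and time standardised over city, and state that the odds ratio is conditional on city.
- **Arm-by-city interaction:** leave it exploratory, as in 10.3.

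The change is useful whether or not allocation is blocked within city. City is known for every randomised participant, so no new data are needed. The cost is one model term, one change of procedure, the standardisation step and the changed meaning of the odds ratio, all to be written into the SAP before the data are analysed.
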